5.5. Drug Accountability, Therapy Compliance and Disposal

The investigator or the site personnel will keep an account of the trial medication and acknowledge the receipt of all shipments of the trial medication. Trial medication will be ordered by the investigator and delivered by the Wirkstoffpeptidlabor to the pharmacy of the participating center. The investigator will document the date of dispensary, subject identification, batch/serial numbers or other identification of trial medication. Upon completion or termination of the study, all unused “mixing kits” have to be returned to the Wirkstoffpeptidlabor of the Department of Immunology. The returned products must be accompanied by adequate documentation and identified clearly with trial site and patient number. The return of any unused study medication must be coordinated by the responsible study monitor/study nurse/pharmacy. Empty packaging does not have to be returned. The disposal is in the responsibility of the study center according to the German laws and local and institutional guidelines and procedures for litter disposal.

In case of SAEs related to the vaccination peptides or adjuvant, the study medication will be returned to the Wirkstoffpeptidlabor of the Department of Immunology, Tübingen for further analysis. The returns will be documented according to SOP.

The returned charges will be locked and deleted according to SOP. A declassification of a drug for clinical use for an application in *in vitro* research experiments is not touched by the declaration. This declassification will be documented. Unused charges of vaccination peptides will be returned to the Wirkstoffpeptidlabor of the Department of Immunology, Tübingen and will be stored.

All waste will be discharged according to German waste laws (date of issue 27.09.1994).

The IMP CoVac-1 may only be applied to subjects included in the P-pVAC-SARS-CoV-2 trial. Other individuals must not receive peptides produced for the P-pVAC-SARS-CoV-2 trial.

Investigational products must be dispensed only by trained and authorized personnel according to legal regulations. Physicians outside the study facility may not apply the study drugs.

5.6. Method of Treatment Assignment

After screening and enrolment, volunteers will be assigned to treatment with CoVac-1.

Protocol		
Protocol code and Short Title:	P-pVAC-SARS-CoV-2	Date/Version:08.03.2021/V1.4

5.7. Dose Schedule

The CoVac-1 vaccine (500 µl) will be administered subcutaneously. Emulsification will be performed by the pharmacy of the participating center according to the “Anweisung Montanide-Emulsion” provided with the “Mixing Kit” by the Wirkstoffpeptidlabor of the Department of Immunology Tübingen. Final vaccine drug product has to be stored at room temperature and to be administered within 24 h after mixing of the components. For qualification of the pharmacy and study center staff regarding ordering and mixing of the peptide vaccine cocktail with Montanide ISA 51 VG, a controlled dry run process will be performed.

The mixing of the peptide vaccine cocktail and Montanide ISA 51 VG will be performed by local pharmacy and the investigator will be provided with a syringe containing the final drug product CoVac-1. A subcutaneous injection of 500 µl (approx. 250 µg per peptide, 50µg XS15) will be applied. A single vaccination per patient will be conducted.

Vaccination instruction

Peptide vaccines should be injected into the skin at the lower part of the abdomen of the volunteers. The site of vaccination (right or left) will be determined by the investigator. At investigator's discretion antihistamines such as 4 mg dimetindene can be applied as i.v. injection or infusion about 30 minutes prior to application of the vaccine.

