5.7.2. Side effects

5.7.2.1. Side effects of peptide vaccination

Peptide vaccination is generally well tolerated. Mild reactions at local vaccination sites are the most common side effects, followed by fatigue^{102 112}. Peptide vaccination can lead to immediate anaphylactic reactions with elevation of heart rate, hyperhidrosis and subjective feeling of dizziness, in rare cases with concomitant drop in blood pressure^{83 83 102}. Cutaneous erythema at the vaccination site was observed more frequently and may persist for up to five weeks. Also, there is a risk of granuloma formation. Some of the patients reported one episode of fever not lasting more than two days. No grade III or IV toxicities were observed in former peptide

Protocol		
Protocol code and Short Title:	P-pVAC-SARS-CoV-2	Date/Version:08.03.2021/V1.4

vaccination studies, including an early trial with a peptide based malaria vaccine, which only reported mild local reactions in approximately 50% of volunteers^{83 99 102}. Furthermore, no signs for the development of antibody-dependent enhancement (ADE) was reported. Of note, side effects in the reported studies are most likely attributable to the applied adjuvants.

In our ongoing iVAC-CLL01 study using peptide cocktails, most of the patients experienced mild local skin reactions at the vaccination site. No anaphylactic or allergic reaction, or other AE related to the peptide vaccine was observed.

Preliminary safety results of volunteers (n = 12) in part I of the P-pVAC-SARS-CoV-2 study showed as intended and expected developed a local granuloma at injection site in all volunteers (100%). Further local injection site adverse events included transient erythema (100%), swelling (100%), itching (83%), pain (58%) and skin ulceration (8%). Until day 28 no relevant systemic side effects, especially no fever or other inflammatory reactions were reported. No allergic reactions were observed. In some participants fatigue (25%), headache (16%), nausea (16%), myalgia (8%) and arthralgia (8%) were reported.

In the P-pVAC-SARS-CoV-2 study, patients will be monitored for heart rate, blood pressure, temperature and subjective well-being after vaccination for at least 2 hours. The volunteers will be discharged after documentation of these parameters. More detailed information on CoVac-1 vaccine peptides is provided with the current IB (Version 1.0).

5.7.2.2. *Side effects of XS15*

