The investigator will review all information obtained from the screening procedures via an eligibility form. The investigator will confirm, in writing, whether the subject fulfils all criteria for eligibility. Volunteers who fulfil all the inclusion criteria and none of the exclusion criteria will be eligible to participate in the trial. Screening failures, i.e. screened volunteers not in compliance with all criteria, are to be excluded and the reason will be recorded in the volunteer records. Information of volunteer's trial participation can be provided to the volunteer's general practitioner if the volunteer agrees.

6.1.3. *Enrolment*

A volunteer is considered for screening when he or she has signed the Informed Consent form.

In case of confirmation of volunteer's eligibility (volunteers must meet all inclusion criteria and must not meet any exclusion criteria), volunteer will be registered under a specific Vol. ID on a subjects log kept at the trial site. Only these volunteers are enrolled in the study, all others are assessed as screening failures.

The study is open-label.

6.1.4. *Randomisation*

No randomisation will be done in this clinical trial.

6.1.5. *Concomitant Medication and Treatments*

Relevant additional medications and treatments administered to the subjects on entry to the trial or at any time during the trial are regarded as concomitant medications and treatments and must be documented on the appropriate pages of the CRF.

6.1.6. *Permitted Prior and Concomitant Medications and Treatments*

The following concomitant medications and treatments are permitted during the trial.

Part I: No concomitant medication, apart from contraception for FCBP.

Part II : Any concomitant medication (already applied at screening) for e.g. other diseases are allowed except for medications stated in section 6.1.7.

6.1.7. *Prohibited Prior and Concomitant Medications and Treatments*

The following concomitant medications and treatments are prohibited during the trial:

Protocol		
Protocol code and Short Title:	P-pVAC-SARS-CoV-2	Date/Version:08.03.2021/V1.4

- Immunosuppressive agents apart from (≤ 10 mg prednisolone or equivalent)
- During the trial, other vaccinations or non-urgent medical interventions are prohibited. Initiation of new medications, regardless of indication must be discussed with the investigator and must be noted on the participant's record.

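### Section 5.7 permits a discretionary antihistamine before vaccination that section 6.1.6 does not provide for, and no planned safety summary shows how many volunteers received it

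*Supplement*

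**What the plan says.** All references are to protocol V1.4; no separate analysis plan is shown.

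- **Premedication.** The vaccination instruction in section 5.7 leaves it to the investigator whether to premedicate: "antihistamines such as 4 mg dimetindene can be applied as i.v. injection or infusion about 30 minutes prior to application of the vaccine". It gives no criterion for use and is not restricted to one Part.
- **Permitted medication.** Section 6.1.6 states "Part I: No concomitant medication, apart from contraception for FCBP". For Part II it states "Any concomitant medication (already applied at screening) for e.g. other diseases are allowed except for medications stated in section 6.1.7".
- **New medication.** Section 6.1.7 prohibits immunosuppressants above a low steroid dose, other vaccinations and non-urgent interventions. Antihistamines are not named. It adds: "Initiation of new medications, regardless of indication must be discussed with the investigator and must be noted on the participant's record".
- **Recording.** Section 6.1.5 requires relevant additional medication to be documented in the CRF. Table 1 and section 6.2.1 schedule a concomitant medication assessment at Visit 1, the vaccination visit.
- **Events of interest.** Section 5.7.2.1 warns: "Peptide vaccination can lead to immediate anaphylactic reactions". Section 9.1.2 lists itching at the injection site and fatigue among the solicited events. For the 12 Part I volunteers, section 5.7.2.1 reports no allergic reactions, itching in 83% and fatigue in 25%.
- **Analysis.** Section 8.3 describes toxicity by absolute and relative frequencies. Section 8.4 plans subgroups by Part only.

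**The concern.** The primary endpoint (section 2.1.1) is the nature, frequency and severity of adverse events associated with CoVac-1. Section 6.2 has every volunteer watched for at least two hours after injection, so an antihistamine given about half an hour beforehand would be a second drug on board during that window. If some volunteers had it, the safety tables describe two conditions: CoVac-1 alone, and CoVac-1 after an antihistamine. The reader could not tell which condition a given frequency refers to.

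The protocol itself treats medication around the injection as relevant to reactogenicity. Section 1.1.5.3 sets CoVac-1 against another vaccine whose trial participants were advised to take paracetamol to lessen reactions. It says no investigator-initiated drug was needed to treat CoVac-1 side effects, which does not answer whether an antihistamine was given in advance.

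What is at stake is how far the trial can say that allergic and reactogenicity findings belong to the vaccine by itself. The absence of allergic reactions in Part I (sections 1.1.5.1 and 5.7.2.1) is part of the safety account put forward for opening Part II.

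**Working it through.** **The plan's own figures.** Section 8.1.1 uses 33 evaluable volunteers, P0 = 0.0001 and P1 = 0.05, with rejection at one or more associated SAEs.

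- Significance level: 1 − 0.9999^33 = 0.0033 (stated 0.003).
- Power: 1 − 0.95^33 = 0.816 (stated 81.6%).
- Enrolment: 33/(1 − 0.075) = 35.7, so 36 (stated 36).

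All three reproduce and none is disputed here.

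**The sections side by side.**

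| | 5.7 | 6.1.6 | 6.1.7 | Result if the option is used |
|---|---|---|---|---|
| Part I (n = 12) | permitted | nothing but contraception | new medication after discussion | outright conflict with 6.1.6 |
| Part II (n = 24) | permitted | only drugs in use at screening | new medication after discussion | not on the permitted list, but 6.1.7 leaves a route |

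**From record to report.** Sections 6.1.5 and 6.2.1 and Table 1 should put any premedication into the database. Sections 8.3 and 8.4 never draw on it. The interim text gives no count for Part I, not even zero.

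**Illustration of the denominator.** With zero events in n volunteers, the exact one-sided 95% upper limit is 1 − 0.05^(1/n). The share premedicated is an assumption, because the documents give none.

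| Share premedicated (assumed) | Part I: n without premedication | Limit | All 36: n without premedication | Limit |
|---|---|---|---|---|
| 0% | 12 | 1 − 0.05^(1/12) = 22.1% | 36 | 1 − 0.05^(1/36) = 8.0% |
| 25% | 9 | 1 − 0.05^(1/9) = 28.3% | 27 | 1 − 0.05^(1/27) = 10.5% |
| 50% | 6 | 1 − 0.05^(1/6) = 39.3% | 18 | 1 − 0.05^(1/18) = 15.3% |
| 75% | 3 | 1 − 0.05^(1/3) = 63.2% | 9 | 1 − 0.05^(1/9) = 28.3% |

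These limits show how much precision a statement about CoVac-1 alone would lose. They do not estimate a bias. They count premedicated volunteers as giving no information on the unpremedicated condition, which is the most cautious reading. The Part I result, zero in 12, is reported; zero in 36 is hypothetical.

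**The case against.** The case against has real force.

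- **Section 5.7 is a permission, not an instruction.** A reader might infer that 5.7 and 6.1.6 cannot both be followed. They can: an investigator who gives no antihistamine complies with both. The conflict arises only on use. In Part II, section 6.1.7 softens it further. This stands.
- **Use is recorded.** A reader might infer that the mix of conditions is unknown in the data. Medication must be documented and is assessed at Visit 1, so it should be possible to count it. The mix is left open by the protocol and absent from the planned analysis, which is a narrower fault. This stands.
- **Part I is finished.** Section 1.1.5 says it was completed in February 2021, before V1.4. Changing its rule alters no conduct. But the same two sentences already stood in V1.2 of October 2020, before recruitment began, so the question of what Part I volunteers received remains open for reporting.
- **A table split is often left to the analysis plan.** That is a reason to put the request there. It does not settle the textual conflict, which lies in the protocol.
- **Bias is not documented.** A reader might infer that allergic signs and itching are understated, fatigue overstated, and premedication aimed at volunteers thought likely to react. No section supports the direction, the selectivity or even the use. Known hypersensitivity to vaccine components is an exclusion, solicited events run for 28 days after a single premedication, and Part I still recorded itching in 83%. This stands.
- **The confirmatory rule.** It counts associated SAEs. Nothing in the documents shows that an antihistamine would change that count, and Part II was opened after DSMB review of the wider safety data. This stands.

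**Conclusion.** The point holds in a limited form. Sections 5.7 and 6.1.6 conflict outright for Part I if the option is used, and more weakly for Part II once 6.1.7 is read with them. The safety analysis pools premedicated and unpremedicated volunteers and splits only by Part, so a statement that no allergic reactions occurred lacks the denominator needed to apply it to CoVac-1 alone.

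Its size cannot be derived from the documents. The upper limit for Part I is 22.1% if nobody was premedicated and 39.3% if 6 of 12 were; for zero events in all 36 it would be 8.0% or, with half premedicated, 15.3%. The half share is an illustration only. If nobody was premedicated, one sentence saying so closes the reporting question, and only the wording conflict remains.

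It would go too far to say that the safety objective is invalid, that results are biased in a known direction, or that any difference between the Parts could be due to premedication alone, since the Parts differ by design in age and health. The conclusion assumes that Visit 1 records capture an antihistamine given on the day of vaccination.

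**What to change.** 1. Reconcile sections 5.7, 6.1.6 and 6.1.7 so that each Part has one consistent rule. This review takes no position on whether premedication should be given.
2. From the recorded Visit 1 medication, report the number premedicated in each Part, including the Part I data already collected, and state zero if it is zero. If the current eCRF page does not separate premedication from other medication, add one field for yes/no, product and time.
3. Tabulate immediate or allergic reactions, itching and fatigue both for all vaccinated volunteers and by premedication status.
4. Beside any statement that no allergic reaction occurred, give the unpremedicated denominator and its exact one-sided 95% upper limit.

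The cost is at most one eCRF field and one split of existing descriptive tables, with no change to sample size, the SAE rule or the schedule. The drawback is a smaller denominator and a wider interval for statements about CoVac-1 alone; keeping the overall table alongside preserves the result for the vaccine as given.

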5.7.1. Dose modifications for peptide vaccine

No dose modification is planned in this trial.

5.7.2. Side effects

5.7.2.1. Side effects of peptide vaccination

Peptide vaccination is generally well tolerated. Mild reactions at local vaccination sites are the most common side effects, followed by fatigue^{102 112}. Peptide vaccination can lead to immediate anaphylactic reactions with elevation of heart rate, hyperhidrosis and subjective feeling of dizziness, in rare cases with concomitant drop in blood pressure^{83 83 102}. Cutaneous erythema at the vaccination site was observed more frequently and may persist for up to five weeks. Also, there is a risk of granuloma formation. Some of the patients reported one episode of fever not lasting more than two days. No grade III or IV toxicities were observed in former peptide

Protocol		
Protocol code and Short Title:	P-pVAC-SARS-CoV-2	Date/Version:08.03.2021/V1.4

vaccination studies, including an early trial with a peptide based malaria vaccine, which only reported mild local reactions in approximately 50% of volunteers^{83 99 102}. Furthermore, no signs for the development of antibody-dependent enhancement (ADE) was reported. Of note, side effects in the reported studies are most likely attributable to the applied adjuvants.

In our ongoing iVAC-CLL01 study using peptide cocktails, most of the patients experienced mild local skin reactions at the vaccination site. No anaphylactic or allergic reaction, or other AE related to the peptide vaccine was observed.

Preliminary safety results of volunteers (n = 12) in part I of the P-pVAC-SARS-CoV-2 study showed as intended and expected developed a local granuloma at injection site in all volunteers (100%). Further local injection site adverse events included transient erythema (100%), swelling (100%), itching (83%), pain (58%) and skin ulceration (8%). Until day 28 no relevant systemic side effects, especially no fever or other inflammatory reactions were reported. No allergic reactions were observed. In some participants fatigue (25%), headache (16%), nausea (16%), myalgia (8%) and arthralgia (8%) were reported.

In the P-pVAC-SARS-CoV-2 study, patients will be monitored for heart rate, blood pressure, temperature and subjective well-being after vaccination for at least 2 hours. The volunteers will be discharged after documentation of these parameters. More detailed information on CoVac-1 vaccine peptides is provided with the current IB (Version 1.0).

5.7.2.2. *Side effects of XS15*

The TLR 1/2 ligand XS15 will be administered subcutaneously together with the SARS-CoV-2 specific peptides emulsified in Montanide ISA 51 VG. XS15 was never used in a clinical trial before. Common side effects of other TLR ligands used for peptide vaccination are reported to be usually mild, comprising local skin reactions, fatigue, flu-like symptoms like fever, muscular pain and aigue. TLR ligands can worsen pre-existing autoinflammatory skin disorders.

Previous application of XS15 in a healthy volunteer and cancer patients (within the scope of individual healing attempts) did, besides local reactions at the vaccination site including formation of granuloma, not cause relevant systemic side effects, in particular no allergic or anaphylactic reactions. More detailed information on XS15 is provided with the current IB (1.0. 27 May 2020).

5.7.2.3. *Side effects of Montanide ISA 51 VG*

Montanide ISA51 is an oil adjuvant suitable for human injection that will be administered together with the SARS-CoV-2 specific peptides and XS15 subcutaneously. Montanide ISA 51 VG was used as an adjuvant in more than 100 peptide vaccination. Most common side effects

Protocol		
Protocol code and Short Title:	P-pVAC-SARS-CoV-2	Date/Version:08.03.2021/V1.4

are injection site reaction (68%) including granuloma development, fatigue (54%), fever (41%), gastrointestinal disorders (32%) and injection site or local erythema (28%)⁸⁹. In general, the observed AEs from controlled trials involving non-healthy as well as healthy individuals were mild to moderate in intensity. Further side effects rarely reported were erythema nodosum (2/36 patients, 5%)¹¹³ and the development of sterile abscesses at injection site (10%)⁸⁹⁻⁹¹.

More detailed information on Montanide ISA 51 VG is provided with the current IB (Version 3291/GB/03/June 2019).

6. Study Procedures and Examination Method

This study will consist of the following consecutive phases: Study entry, vaccination/treatment and follow-up. Time-points and trial procedures are listed in Table 1.

6.1. Study Entry

6.1.1. *Volunteer's Informed Consent*

Subjects are informed both in writing and verbally by the investigator before any study-specific procedure is performed. Each volunteer will be informed about the modalities of the clinical study in accordance with the provided volunteer information. The volunteer is given sufficient time (≥ 24 h) to consider participation in the clinical trial and to ask for additional advise if needed. Informed consent from the volunteer will be obtained using a form approved by the responsible EC. The volunteer and informing investigator must each personally date and sign the informed consent form containing an integrated declaration on data privacy protection. The original signed document will be part of the investigator's site file and retained with it, a copy including the insurance policy of the trial will be handed to the volunteer. The informed consent process is documented in the volunteer records.

6.1.2. *Screening*

Screening will be performed within *one week* (7 days) prior to the administration of the CoVac-1 vaccine. After having signed the informed consent form, volunteers will undergo all assessments listed below:

- Demographics
- Medical history
- Enrolment
- Vital signs
- Physical examination
- Concomitant medications
- Hematology (local lab)
- Blood chemistry and coagulation (local lab)
- Urine analysis (local lab)
- Immunoglobulins/Immunophenotype (local lab), approximately 10 ml blood
- Testing for previous or current SARS-CoV-2 infection: 5ml serum blood will be drawn for antibody testing and a nose/throat swab* will be performed.
- HBV, HCV, HIV-1, (local lab)

Protocol		
Protocol code and Short Title:	P-pVAC-SARS-CoV-2	Date/Version:08.03.2021/V1.4

- Pregnancy test

* If screening takes more than 48 hours, throat/nose swab for SARS-CoV-2 infection must be repeated. The vaccine can only be applied if a negative SARS-CoV-2 PCR test is available on the day of vaccination not older than 48 hours.

The investigator will review all information obtained from the screening procedures via an eligibility form. The investigator will confirm, in writing, whether the subject fulfils all criteria for eligibility. Volunteers who fulfil all the inclusion criteria and none of the exclusion criteria will be eligible to participate in the trial. Screening failures, i.e. screened volunteers not in compliance with all criteria, are to be excluded and the reason will be recorded in the volunteer records. Information of volunteer's trial participation can be provided to the volunteer's general practitioner if the volunteer agrees.

6.1.3. *Enrolment*

A volunteer is considered for screening when he or she has signed the Informed Consent form.

In case of confirmation of volunteer's eligibility (volunteers must meet all inclusion criteria and must not meet any exclusion criteria), volunteer will be registered under a specific Vol. ID on a subjects log kept at the trial site. Only these volunteers are enrolled in the study, all others are assessed as screening failures.

The study is open-label.

6.1.4. *Randomisation*

No randomisation will be done in this clinical trial.

6.1.5. *Concomitant Medication and Treatments*

Relevant additional medications and treatments administered to the subjects on entry to the trial or at any time during the trial are regarded as concomitant medications and treatments and must be documented on the appropriate pages of the CRF.

6.1.6. *Permitted Prior and Concomitant Medications and Treatments*

The following concomitant medications and treatments are permitted during the trial.

Part I: No concomitant medication, apart from contraception for FCBP.

Part II : Any concomitant medication (already applied at screening) for e.g. other diseases are allowed except for medications stated in section 6.1.7.

6.1.7. *Prohibited Prior and Concomitant Medications and Treatments*

The following concomitant medications and treatments are prohibited during the trial:

Protocol		
Protocol code and Short Title:	P-pVAC-SARS-CoV-2	Date/Version:08.03.2021/V1.4

- Immunosuppressive agents apart from (≤ 10 mg prednisolone or equivalent)
- During the trial, other vaccinations or non-urgent medical interventions are prohibited. Initiation of new medications, regardless of indication must be discussed with the investigator and must be noted on the participant's record.

